11.4.3 Secondary Efficacy Analyses

The proportion of subjects with a $\geq 20\%$ improvement from baseline to Day 29 in the global symptom score from SANDE Part 1 in the 0.017% and placebo arms will be analyzed via logistic regression. The model will include all subjects in the mITT population, and subjects with a $\geq 20\%$ improvement will be considered responders. Subjects with a < 20% improvement will be considered non-responders. Responder status (yes/no) will be the dependent variable in the model, and the model will include the treatment, study site, and baseline SANDE Part 1 global symptom score as fixed effects. A significance test of the treatment difference will be tested at the two-sided 0.05 level, and odds ratios and their corresponding 95% confidence intervals will be calculated. Details regarding the handling of missing data due to early withdrawals or missed assessments will be described in the SAP. The proportion of subjects improving as evaluated using the SANDE Part 2 assessment will be analyzed in a similar manner.

Continuous secondary endpoints including the change from baseline in: the total SPEED symptom score, each of the items from the 7-item symptom questionnaire, total corneal staining score, total bulbar conjunctival staining score, lid wiper area staining score, and TBUT will be analyzed in a similar manner as the primary endpoint. The model will be changed to include the baseline value of the secondary endpoint instead of the baseline SANDE Part 1 global symptom score. Other endpoints, such as the change from baseline in the staining score of certain regions of the cornea, will be explored and analyzed in a similar manner. Further details will be provided in the SAP, along with details on how the change from baseline over the entire 28 day treatment period using the SANDE Part 2 assessment and the definition of improvement over 28 days using the SANDE Part 2 assessment will be defined.

The primary evaluation of interest for secondary endpoints measuring signs of dry eye will utilize the Study Eye. Additional analyses will be performed for all qualifying eyes. Analyses utilizing all qualifying eyes will account for the correlation between eyes within subjects. Total conjunctival and corneal staining scores will be defined as the sum of the scores from all six and five regions, respectively. The staining score of the lid wiper area will be defined as noted in the Study Manual.

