APPENDIX IV: DRY EYE SYMPTOM QUESTIONNAIRES

The following subject-completed symptom assessments will be collected as noted in Appendix I prior to any other clinic assessments to minimize bias.

- SANDE, Part 1 will be conducted at Visits 1, 2, 3, and 4, and Part 2 at Visit 2, 3, and 4.
- SPEED will be conducted at Visits 1, 2, 3, and 4
- 7-item symptom questionnaire will be conducted at Visits 1, 2, 3, and 4

SYMPTOM ASSESSMENT IN DRY EYE QUESTIONNAIRE (SANDE) (Schaumberg, 2007)

Part 1

PLEASE COMPLETE THE FOLLOWING QUESTIONS REGARDING THE FREQUENCY AND SEVERITY OF YOUR DRY EYE SYMPTOMS
1. Frequency of symptoms:
Please place an 'I' on the line to indicate how often , on average, your eyes felt dry and/or irritated over the past day:
Rarely ————————————————————————————————————
2. Severity of symptoms:
Please place an 'I' on the line to indicate how severe , on average, you feel your symptoms of dryness and /or irritation were over the past day:
Very Mild ———— Very Severe

Instructions for scoring; Part 1. Measure the distance (in mm) between the left end of the line and the mark scored by the subject.

Part 2 (administer at only Visits 2, 3, and 4)

PLEASE COMPLETE THE FOLLOWING QUESTIONS REGARDING TREQUENCY AND SEVERITY OF YOUR DRY EYE SYMPTOMS	THE
1. Frequency of symptoms:	
Please place an 'I' on the line to indicate how often, on average, yo dry or irritated now compared to at your last visit approximately 2 was a compared to a compared t	•
Much less Frequent Last Visit	Much more frequent
2. Severity of symptoms:	
Please place an 'I' on the line to indicate how severe, on average, your symptoms of dryness and irritation are now compared to at your approximately 2 weeks ago	•
Much less severe Last Visit	Much more severe

Instructions for scoring; Part 2. Measure the distance (in mm) between the "Last Visit" anchor at the center of the scale and the mark scored by the subject. If the mark is placed to the right of the anchor, the score will be assigned a positive value (e.g. +10). If the mark is to the left of the anchor, the score will be assigned a negative value (e.g. -15)

SPEED QUESTIONNAIRE (Ngo, 2013 and Korb, 2005)

1. Report the type of SYMPTOMS you experience and when they occur:

	At this Visit		Within the past 72 hours		Within past 3 months	
Symptoms	Yes	No	Yes	No	Yes	No
Dryness						
Grittiness or Scratchiness						
Soreness or Irritation						
Burning or Watering						

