5.2.3. Secondary Efficacy Endpoints

The secondary efficacy endpoints for the study are as follows:

- 1. Change from baseline to Day 15 and Day 29 in the SPEED questionnaire total symptom score.
- 2. Changes from baseline to Day 15 and Day 29 in each of the 7-item symptom questionnaire scores.
- 3. Change from baseline to Day 15 and Day 29 in staining of the Lid Wiper area.
- 4. Change from baseline to Day 15 and Day 29 in bulbar conjunctival staining total score.
- 5. Change from baseline to Day 15 and Day 29 in corneal staining total score.
- 6. Changes from baseline to Day 15 and Day 29 in tear breakup time (TBUT).
- 7. Change in symptom frequency score and severity score as recorded by the subject using the SANDE Part 2 assessment.
- 8. Change from baseline to Day 15 and Day 29 in the SANDE symptom frequency and

CONFIDENTIAL Page 16 08 August 2017

- severity scores from Part 1.
- 9. The proportion of subjects with at least a 20% improvement from baseline to Day 15 and Day 29 in the SANDE global symptom score from Part 1 (and in the frequency and severity scores).
- 10. The proportion of subjects with at least a 10% improvement over 14 days from Day 1 to Day 15 and from Day 15 to Day 29 in symptom frequency score and severity score using the SANDE Part 2 assessment.

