5. Corneal staining total score is defined as the sum of scores from 5 regions: Central, Superior, Temporal, Nasal, and Inferior. The score for each region ranges from 0 to 3. Thus, the corneal staining total score can range from 0 to 15. The change from baseline to Day 29 will be analyzed in a similar manner as the Change from baseline to Day 29 in staining of the Lid Wiper area. A secondary analysis will be performed assessing the change from baseline at Day 15.

CONFIDENTIAL Page 18 08 August 2017

The descriptive statistics for change from screening to baseline will be presented by treatment.

The analysis will be repeated for the inferior region (region 5) individually.

Mean and 95% CI for corneal staining total scores will be plotted by treatment and study visit.

6. The change from baseline to Day 29 in TBUT (seconds) will be analyzed in a similar manner as the Change from baseline to Day 29 in staining of the Lid Wiper area. A secondary analysis will be performed assessing the change from baseline at Day 15.

The descriptive statistics for change from screening to baseline will be presented by treatment.

Mean and 95% CI of TBUT will be plotted by treatment and study visit.

7. The SANDE Part 2 is comprised of two 100mm VAS scales. One measures the frequency of symptoms at the current visit as compared to the frequency of symptoms at the previous visit. The score ranges from much less frequent (-50) to much more frequent (50). The second VAS measures the severity of symptoms at the current visit as compared to the severity of symptoms at the previous visit. The score ranges from much less severe (-50) to much more severe (50).

The change from previous visit for frequency and severity of symptoms will be summarized individually by treatment at Day 1, Day 15, and Day 29. Differences between the 0.017% P-321 treatment group and placebo will be assessed using a mixed model repeated measures analysis with fixed effects for treatment and study site, visit, and visit by treatment interaction. The following 3 covariance structures will be considered: AR(1), CS, and UN. The covariance structure with the lowest AIC will be selected.

Additionally, the proportion of subjects with improvement from previous visit, no change from previous visit, and worsening from previous visit at Day 1, Day 15, and Day 29 will be summarized by treatment group and overall.

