8. The SANDE Part 1 is comprised of two 100mm VAS scales. One measures frequency of symptoms from rarely (0) to all the time (100). The other measures severity of symptoms from very mild (0) to very severe (100). The change from baseline to Day 29 in the SANDE symptom frequency and severity scores from Part 1 will be analyzed individually in a similar manner as the primary endpoint. A secondary analysis will be performed assessing the change from baseline at Day 15.

Additionally, the proportion of subjects with improvement from baseline, no change from baseline, and worsening from baseline to Day 29 will be summarized by treatment group and overall. The analysis will be repeated at Day 15

CONFIDENTIAL Page 19 08 August 2017

- 9. Subjects whose SANDE global symptom score from Part 1 decreases by 20% or more from baseline to Day 29 will be considered responders. Subjects whose scores do not decrease by 20% or more will be considered non-responders. Differences between the proportion of responders between the 0.017% P-321 treatment group and placebo will be assessed using a logistic regression model with fixed effects for treatment, study site, and baseline value. The odds ratio and corresponding 95% confidence interval will be presented. The analysis will also be performed for the frequency and severity scores individually. A secondary analysis will be performed assessing the change from baseline at Day 15.
 - A Sensitivity analysis will be performed where all subjects with missing data will be considered non-responders.
- 10. A 10% or more improvement from previous visit will be defined as a SANDE Part 2 value of 5 or more. Subjects whose scores show an improvement of symptoms by 10% or more from baseline to Day 15 will be considered responders at Day 15. Subjects whose scores show an improvement of symptoms by 10% or more from Day 15 to Day 29 will be considered responders at Day 29. Differences between the proportion of responders between the 0.017% P-321 treatment group and placebo will be assessed separately at Day 15 and at Day 29 using a logistic regression model with fixed effects for treatment and study site.

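### The SANDE Part 2 responder rule in SAP 5.2.4 item 10 has the wrong sign: as written it counts worsening of 5 mm or more as improvement

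*SAP*

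**What the plan says.** Secondary endpoint 10 (SAP 5.2.3) is the share of subjects in each arm who improve by 10% or more on Part 2 across each two-week interval, first to Day 15 and then on to Day 29, for the frequency and severity scores. SAP 5.2.4, item 10, gives the numeric rule: "A 10% or more improvement from previous visit will be defined as a SANDE Part 2 value of 5 or more". Responders are then compared between arms at each of the two visits by logistic regression with treatment and site.

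The direction of the Part 2 scale is set in two other places, and they agree:

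- SAP 5.2.4, item 7, on frequency: "The score ranges from much less frequent (-50) to much more frequent (50"; on severity: "The score ranges from much less severe (-50) to much more severe (50".
- Protocol Appendix IV, scoring instructions for Part 2, on marks to the right: "If the mark is placed to the right of the anchor, the score will be assigned a positive value (e.g. +10"; and on marks to the left: "If the mark is to the left of the anchor, the score will be assigned a negative value (e.g. -15". The left end of each line is the *much less* end and the right end is the *much more* end.

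The protocol sets no Part 2 cut-off of its own. Section 11.4.3 says that "the definition of improvement over 28 days using the SANDE Part 2 assessment will be defined" in the SAP.

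**The concern.** On the scale that both documents define, a subject who feels better scores below zero. Item 10 calls a value of +5 or above an improvement, so it selects subjects who report being worse by at least 5 mm and excludes every subject who reports being better.

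The rule feeds four planned models (two scores at two visits) and Tables 14.2.11.1 and 14.2.11.2, both titled as proportions improving. If the drug moves scores towards the *less* end, fewer drug subjects pass the rule and the treatment comparison points the wrong way. The report would also contradict itself, because the item 7 mixed model of the same scores would show the benefit as more negative means.

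Part 2 is a visible instrument in this trial: protocol 11.2 and SAP 3.1 base the sample size on the Part 2 global score from the previous study.

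**Working it through.** **1. Size of the cut-off.** Each Part 2 line is 100 mm with the anchor at the centre, so each half runs 50 mm. Ten percent of the half-scale is 0.10 × 50 = 5 mm, which matches the SAP. Ten percent of the whole line would be 0.10 × 100 = 10 mm, which does not. The SAP therefore intends 5 mm on the half-scale, and the size is not in dispute.

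**2. Direction of the cut-off.**

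| Source | Better than last visit | Worse than last visit |
|---|---|---|
| Protocol Appendix IV | left of anchor, negative | right of anchor, positive |
| SAP 5.2.4 item 7 | down to -50 | up to +50 |
| SAP 5.2.4 item 10 | +5 or above | not stated |

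Item 10 is the odd one out. Reading its 5 as an absolute value does not help, because improvement and worsening would then both count as response. No recoding step appears in the SAP. Item 9, for Part 1, has the direction right: "Subjects whose SANDE global symptom score from Part 1 decreases by 20% or more from baseline to Day 29 will be considered responders".

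**3. Effect on the result.** For a score X with mean m and standard deviation SD, assumed normal:

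- rule as written: P(X ≥ 5) = 1 − Φ((5 − m)/SD)
- corrected rule: P(X ≤ −5) = Φ((−5 − m)/SD)

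Clipping scores at ±50 leaves both probabilities unchanged.

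*Illustration A.* SD 22 and a difference of 20 are taken from SAP 3.1, where they describe the Part 2 global score. The placebo mean of 0 is an assumption, which puts the drug mean at -20.

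- As written, placebo: 1 − Φ(5/22) = 1 − Φ(0.227) = 41.0%. Drug: 1 − Φ(25/22) = 1 − Φ(1.136) = 12.8%. Odds ratio (0.128/0.872)/(0.410/0.590) = 0.21.
- Corrected, placebo: Φ(−5/22) = 41.0%. Drug: Φ(15/22) = Φ(0.682) = 75.2%. Odds ratio 4.37, from unrounded proportions.

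With 30 per arm, a simple two-sided 5% comparison of 41.0% with 12.8%, ignoring site, has a standard error of √(2 × 0.269 × 0.731/30) = 0.1145 under the null and √((0.410 × 0.590 + 0.128 × 0.872)/30) = 0.1085 under the alternative. The power is Φ((0.282 − 1.96 × 0.1145)/0.1085) = Φ(0.53) = 0.70. Under these assumptions there is about a 70% chance of a significant result in the wrong direction.

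*Illustration B.* A smaller effect, with both means assumed: placebo -5, drug -15.

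| SD | As written: placebo v drug | Corrected: placebo v drug |
|---|---|---|
| 15 | 25.2% v 9.1% (OR 0.30) | 50.0% v 74.8% (OR 2.96) |
| 22 | 32.5% v 18.2% (OR 0.46) | 50.0% v 67.5% (OR 2.08) |

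*Range.* Over SD 15, 22 and 29, placebo mean 0, -5 and -10, and drug benefit 5, 10 and 20 mm (27 combinations), the odds ratio is 0.05 to 0.76 as written and 1.32 to 11.67 corrected.

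**4. Why the reversal is general.** If treatment moves the whole distribution towards the *less* end, the share at or above +5 cannot rise and the share at or below -5 cannot fall, whatever the shape of the distribution. The figures above only give this a size.

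**The case against.** The strongest reply is that the intent is plain. The rest of item 10, the endpoint in SAP 5.2.3 and the table titles all speak of improvement, and item 9 treats a decrease as response, so 5 could be read as the size of the improvement. SAP section 5 also requires independent programming and verification by the lead statistician, and a reversed item 10 would clash visibly with item 7. This stands in part: the harm depends on the rule being coded as written. But inferring the intent means departing from the only number the SAP gives, and two programmers who follow the same sentence will agree on the same wrong answer.

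Scope is limited, and that stands in full. This is one of ten secondary endpoint groups. The SAP plans no multiplicity adjustment and describes no testing hierarchy, so no other test depends on it.

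The reversal is also not certain under every distribution. With placebo mean 0 and SD 10 against drug mean -5 and SD 25 (all assumed), the rule as written gives 31% v 34%, so the benefit would not appear as harm. Even then, the subjects counted are those who worsened.

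Finally, item 10 does not itself promise an odds ratio. That comes from item 9 and from protocol 11.4.3, which has the Part 2 proportions analysed like the Part 1 responders.

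**Conclusion.** The concern holds. The sign in item 10 contradicts SAP item 7 and protocol Appendix IV, and no other text corrects it. Applied literally, the rule mislabels worsening as improvement under any assumption, and it generally reverses the treatment comparison. The percentages and odds ratios rest on assumed normal scores and assumed means, with a standard deviation and difference borrowed from the global score rather than from the separate frequency and severity scores; they show direction and are not forecasts.

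Only secondary endpoint 10 is affected. The primary endpoint (Part 1 global score), the Part 2 mixed model in item 7, the Part 1 20% responder analysis and the sample size are untouched. It should still be corrected before unmasking, because the rule is wrong in direction rather than debatable in degree.

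**What to change.** Reword item 10 so that a 10% or greater improvement from the previous visit is a SANDE Part 2 value of -5 or less, that is, a mark at least 5 mm to the left of the Last Visit anchor. State in item 7 that negative values are improvement, zero is no change and positive values are worsening, so that the three-category table uses the same direction. Check that the programs for Tables 14.2.11.1 and 14.2.11.2 follow the corrected rule.

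The cost is one line of SAP text, one clarifying line in item 7 and the matching program line. After unmasking the same change would have to be reported as a deviation under SAP section 7, and reversing a responder definition at that stage could look driven by the results.

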5.2.2 Secondary Efficacy Endpoints

Secondary efficacy endpoints include:

- Change from baseline to Day 29 in the SPEED questionnaire total symptom score
- Changes from baseline to Day 29 in each of the 7-item symptom questionnaire scores (see Appendix)
- Change from baseline to Day 29 in staining of the Lid Wiper area
- Change from baseline to Day 29 in bulbar conjunctival staining total score
- Change from baseline to Day 29 in corneal staining total score
- Changes from baseline to Day 29 in TBUT
- Change in symptom frequency score and severity score as recorded by the subject using the SANDE Part 2 assessment

- Change from baseline to Day 29 in the SANDE symptom frequency and severity scores from Part 1
- The proportion of subjects with at least a 20% improvement from baseline to Day 29 in the SANDE global symptom score from Part 1 (and in the frequency and severity scores)
- The proportion of subjects with an improvement following 28 days of treatment in symptom frequency score and severity score using the SANDE Part 2 assessment

Changes from baseline to Day 15 will also be assessed.

Exploratory assessments include biomarkers of inflammation in tears and from impression cytology samples collected from the lid wiper and the bulbar conjunctiva.

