11.4 Analysis of Efficacy

11.4.1 Efficacy Endpoints

Analyses of efficacy will be conducted using the Study Eye. A supportive efficacy analysis will be also conducted on all qualifying eyes, as defined in the Statistical Analysis Plan. Analyses of efficacy conducted on all qualifying eyes will account for the correlation between eyes within subjects with two qualifying eyes.

Primary Efficacy Endpoint:

The mean change from baseline (Visit 2) to Day 29 (Visit 4) in the SANDE questionnaire global symptom score from Part 1. The primary efficacy comparison will be the mean change from baseline in the SANDE global symptom score for the 0.017% treatment arm compared to placebo.

Secondary Efficacy Endpoints:

- Change from baseline to Day 29 in the SPEED questionnaire total symptom score
- Changes from baseline to Day 29 in each of the 7-item symptom questionnaire scores
- Change from baseline to Day 29 in staining of the Lid Wiper area
- Change from baseline to Day 29 in bulbar conjunctival staining total score
- Change from baseline to Day 29 in corneal staining total score
- Changes from baseline to Day 29 in TBUT
- Change in symptom frequency score and severity score as recorded by the subject using the SANDE Part 2 assessment
- Change from baseline to Day 29 in the SANDE symptom frequency and severity scores from Part 1
- The proportion of subjects with at least a 20% improvement from baseline to Day 29 in the SANDE global symptom score from Part 1 (and in the frequency and severity scores)
- The proportion of subjects with an improvement over 28 days in symptom frequency score and severity score using the SANDE Part 2 assessment
- Changes from baseline to Day 15 will also be assessed for all efficacy measurements.

Parion Sciences, Inc.
Protocol P-321-202 Amendment 01

Exploratory Efficacy Endpoints:

Changes from baseline in biomarkers of inflammation in tears and from impression cytology samples collected from the lid wiper and the bulbar conjunctiva.

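### SAP 5.2.4 scores SANDE Part 2 response with the wrong sign in item 10, and neither item 7 nor item 10 states the 28-day Part 2 result that the protocol assigns to the SAP

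*SAP*

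**What the plan says.** **Protocol.** Section 5.2.2 lists as a secondary endpoint the proportion of subjects with "an improvement following 28 days of treatment in symptom frequency score and severity score" on SANDE Part 2. Section 11.4.1 repeats it: "The proportion of subjects with an improvement over 28 days in symptom frequency score and severity score using the SANDE Part 2 assessment". Section 11.4.3 assigns two tasks to the SAP: how the Part 2 change over the whole 28-day period is derived, and "the definition of improvement over 28 days using the SANDE Part 2 assessment will be defined".

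**Instrument.** In Appendix IV, Part 2 asks for symptoms now "compared to at your last visit approximately 2" weeks ago. The right end of each line is more frequent or more severe, and the scoring note says: "If the mark is placed to the right of the anchor, the score will be assigned a positive value". SAP 5.2.4 item 7 keeps this direction, from -50 (much less) to +50 (much more).

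**SAP.**
- Section 5.2.3, endpoint 10, is the proportion with "at least a 10% improvement over 14 days from Day 1 to Day 15 and from Day 15 to Day 29".
- Section 5.2.4, item 10, sets the 10% improvement at a Part 2 score of +5 or higher. Subjects who improve "by 10% or more from Day 15 to Day 29 will be considered responders at Day 29". Days 15 and 29 are tested separately by logistic regression.
- Section 5.2.4, item 7, summarizes the change from the previous visit at Days 1, 15 and 29 and assesses treatment differences with a "mixed model repeated measures analysis with fixed effects for treatment and study site, visit, and visit by treatment interaction". It names no visit, average or sum as the estimate.
- Section 10 titles the responder tables (14.2.11.1 and 14.2.11.2) as improvement from the previous visit.
- Section 7 anticipates no change to the planned analysis.

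**The concern.** There are two separate faults.

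The first is the sign. On the documents' own scale, a score of +5 or higher is a worsening. A program that follows item 10 literally counts worsened subjects as responders, and the odds ratio then points against the better arm.

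The second is the missing 28-day quantity. Each Part 2 score spans one interval, so no single score covers baseline to Day 29 and a rule for combining intervals is needed. The protocol asks the SAP for that rule and the SAP gives none. A subject labelled a responder at Day 29 has been judged on the last two weeks only. Item 7 could yield a 28-day estimate, but several readings of it are possible and they give different numbers. SAP 3.3.3 applies no multiplicity adjustment. If the choice is left open, it could be made after results are seen.

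**Working it through.** **1. The cut-off.** The half-scale is 50 mm, and 10% × 50 = 5, so the size of the item 10 cut-off reproduces. The sign does not: under Appendix IV and item 7, an improvement of 10% or more is a score of -5 or lower.

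**2. Two subjects, Visit 3 then Visit 4 score (negative = better).**
- -20 then 0: net -20, better over 28 days, not a Day 29 responder.
- +20 then -6: net +14, worse over 28 days, a Day 29 responder once the sign is corrected.

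Neither example needs an assumption about distributions.

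**3. Illustrative rates.** The documents give no SD for a single Part 2 scale. I assume normal interval scores with SD 15.6 mm and independent intervals. The sum then has SD 15.6 × √2 = 22.06, close to the SD of 22 that SAP 3.1 quotes for a Part 2 global score. The means are also assumed. Take an early gain that is held: active -15 then 0, placebo -5 then 0.

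| Rule | Formula | Active | Placebo |
|---|---|---|---|
| Day 15, -5 or lower | Φ((-5 - mean)/15.6) | Φ(0.641) = 74% | Φ(0) = 50% |
| Day 29, -5 or lower | Φ((-5 - mean)/15.6) | Φ(-0.321) = 37% | Φ(-0.321) = 37% |
| Sum below 0 | Φ((0 - sum of means)/22.06) | Φ(0.680) = 75% | Φ(0.227) = 59% |
| Sum -5 or lower | Φ((-5 - sum of means)/22.06) | 67% | 50% |
| Sum -10 or lower | Φ((-10 - sum of means)/22.06) | 59% | 41% |
| Day 15, item 10 taken literally (+5 or higher) | 1 - Φ((5 - mean)/15.6) | 10% | 26% |

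The Day 29 test shows no difference, while 75% vs 59% have a net improvement. The literal sign turns 74% vs 50% at Day 15 into 10% vs 26%. With a steady effect (-10, -10 vs -2.5, -2.5), it turns 63% vs 44% into 17% vs 32%. A simulation with scores clipped to ±50 agreed within 0.2 points.

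**4. Item 7 in the same gain-held case.** The treatment differences are 0 at Day 1, -15 - (-5) = -10 at Day 15, and 0 at Day 29. Possible readings:
- Day 29 alone: 0 mm
- mean of Days 1, 15 and 29: -10/3 = -3.3 mm
- mean of Days 15 and 29: -10/2 = -5 mm
- 28-day sum: -10 + 0 = -10 mm

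By contrast, SAP 5.2.2 names Day 29 for the primary analysis.

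**5. How often the two classifications disagree.** Let A be a Day 29 score of -5 or lower and B a sum below 0. Disagreement = P(A) + P(B) - 2P(A and B), from the bivariate normal, with SD 13.6 to 22 and correlation ρ from -0.3 to 0.3. The sum has SD = SD × √(2(1 + ρ)). The mean patterns are the gain held and steady cases above, a gain lost (-15, +10 vs -5, 0), and an early worsening partly recovered (+10, -8 vs 0, 0).
- Lowest (+10, -8; SD 22; ρ 0.3): 0.554 + 0.478 - 2 × 0.411 = 0.210.
- Highest (-15, +10; SD 13.6; ρ -0.3): 0.135 + 0.622 - 2 × 0.126 = 0.505.

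Disagreement therefore runs from about 21% to 51% of subjects per arm.

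**6. Precision of the sum, 30 per arm.** One interval: 15.6 × √(2/30) = 4.0 mm. Sum: 15.6 × √2 × √(2/30) = 5.7 mm.

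**The case against.** The strongest reply is that the protocol delegated these definitions and the SAP used the delegation. Part 2 asks only about the last visit, so interval analysis respects the instrument. Item 10 fixes threshold, windows, model and test days, and it reports both tests, so nothing is selected between them. Read together, they show whether an early gain was later lost. The visit-by-treatment term in item 7 allows by-visit differences, which is its natural reading. The words of item 10 after the cut-off speak of improving symptoms, item 7 states the direction, and SAP section 5 requires independent programming, so the sign would probably be caught.

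Much of this stands. A reader might infer that Part 2 has no pre-specified analysis at all, or that results will be reported backwards. The documents support neither: the 14-day tests are specified, and reversal needs literal coding against the evident intent of the same item. It would also go too far to treat SAP section 7 as denying a known departure, because that section chiefly concerns deviations from the SAP itself.

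What does not stand is that delegation settles the matter. Protocol 11.4.3 asks for a 28-day derivation, and two separate 14-day definitions are not one. The two marginal responder rates do not give the proportion with a net improvement.

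**Conclusion.** The point holds in two parts. The item 10 cut-off has the wrong sign on the documents' own scale and must be corrected, even though it is probably a slip. The SAP also omits both 28-day Part 2 definitions left to it, and item 7 neither names a contrast nor says whether the Day 1 run-in score is modelled. These conclusions rest on the text alone.

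The sizes are illustrative. The 37% vs 37% against 75% vs 59%, and the disagreement of about 21% to 51%, depend on assumed means, SDs and correlations.

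A reader might infer that the trial lacks a 28-day symptom result. It does not: the SANDE Part 1 global score (the primary endpoint), its two components and the 20% responder analysis all cover baseline to Day 29. The gap is confined to one secondary instrument and should be closed before unmasking.

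**What to change.** Before unmasking, for frequency and severity separately:

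1. In item 10, change the cut-off to a score of -5 or lower.
2. In item 7, exclude the Day 1 run-in score and name the 28-day estimate as the sum of the Day 15 and Day 29 treatment differences, with its 95% CI.
3. Define 28-day improvement as Visit 3 score plus Visit 4 score below 0. This follows the protocol, which asks for an improvement and sets no threshold. Test it with the item 10 logistic model. Cut-offs of -5 and -10 mm are optional sensitivity analyses.
4. In that responder analysis, treat the sum as missing if Visit 3 or Visit 4 is missed, with non-response as a sensitivity analysis, as item 9 does. State how item 7 treats a Visit 4 score after a missed Visit 3, because the last visit that the subject compares with may then be Visit 2.
5. Keep the 14-day analyses as supportive and label the second as a Day 15 to Day 29 responder.

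If the sponsor means to replace the 28-day endpoint, the minimum is step 1 plus a recorded reason for the difference from the protocol.

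The cost is SAP wording, one contrast and one derived variable per scale, all from data already collected. There are two downsides. Summing assumes that the two comparative ratings add. The sum is also less precise than one interval: standard error 5.7 vs 4.0 mm under the assumptions in the check.
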